COPTR Preparation for Primary Analysis

INTRODUCTION

Determination of the effect of an intervention on the primary outcome is usually the most important analysis in a randomized trial. Therefore, the COPTR investigators have carefully specified the statistical analysis plans for the primary outcome for each of the 4 field site studies. Analysis plans were reviewed and approved by the DSMB in April, 2012 as a part of the review of the study protocols. More recently, the COPTR investigators have taken additional steps to ensure full and detailed specification of variable definitions and the analytic plans that will be used in the final analyses.

The process undertaken involved the simulation of data in which the final primary outcome analysis could be rehearsed. The variables to be used in the analysis and imputation of missing data (when applicable) were defined and constructed. Analytic code was written independently by investigators at study sites and the RCU, analyses were conducted using simulated data, and results were compared. If differences were identified the code from the RCU and the site were compared by an independent programmer and adjudicated. Following this process, the results from the study sites and from the RCU were, for practical purposes, identical.

This primary outcome analysis rehearsal has served as a vehicle to expose detailed decisions and adjustments that needed to be made in analysis plans. The Steering Committee acknowledges that ideally every aspect of the primary analysis would be established before the study begins. However, our protocols, while detailed, did not address every nuance of the analysis and the imputation of missing data. In addition, there can be unanticipated changes in study implementation that invoke refinement of the data analysis plan. It is important to note that, at the time of this report, masking remains firmly in place. All personnel at the sites, including the site statisticians, signed written statements masking them to all analyses by arm.

To support full transparency, we have prepared a summary of the adjustments, clarifications and specifications made to statistical analysis plans during the course of this project (section A), followed by the final revised analysis plan (section B). Revisions to the analysis plans approved in April of 2012 are shown as tracked changes. The descriptions address only the primary analysis and, unless relevant to the revised analysis, we have removed from the text below details related to assumptions, power calculations, and secondary and sensitivity analyses. Deletions were not tracked, but the removal of this type of text is denoted by 3 stars (***)�.

The plans shown below were endorsed by the Steering Committee with 5 votes in favor and one abstention. The NHLBI abstained because of concerns about the Vanderbilt change in the primary outcome test. More details on this discussion are shown below in Section 4 and in the addendum.

The preliminary work on the primary analysis done by the COPTR investigators was more extensive than that usually conducted in trials. The construction of simulated data and the implementation of planned analyses exposed details and concerns that otherwise may not have been addressed until after the blind was broken. We are confident that the expanded process of preliminary analyses conducted by the COPTR investigators will expedite the time required to move the COPTR primary outcomes analyses to full publication.

UNIVERSITY OF MINNESOTA

A2: Summary of adjustments, clarifications and specifications

- The primary analysis will not include a random effect for ECFE cohort membership.
At the time the original SAP was approved by the DSMB, it was our intention that consistent and identifiable cohorts of families would attend a series of Early Childhood and Family Education (ECFE) classes together over the duration of the intervention. This component of the NET-Works intervention did not materialize as intended. ECFE participation was lower than expected and there are not identifiable or consistent groups of families that attend these classes.
- The primary analysis will include a random effect for Family Connector (FC) assignment
It was observed that the home visit component of the NET-Works intervention was delivered to N=257 out of N=265 intervention group families by 7 family connectors. Because it is possible that characteristics of particular FCs may be related to BMI outcomes of the families to which they are assigned, we determined that it would be prudent to model this potential source of dependency in the primary outcome.
The decision to omit the random ECFE term and estimate a random FC term was made after study recruitment was complete and sample size was therefore fixed.
- Family Connector specification
The method for coding the Family Connector was not previously specified. Seven FCs delivered the home visit intervention component to 257 of the 265 treatment group families. Each of these 257 families will be assigned to a FC group based on the primary FC with whom they worked. Treatment group families that did not participate in the home visit intervention component, and all control group families, will be assigned to their own n=1 FC group.
- Multiple imputation specifications
We indicated previously that variables from the analytic model as well as auxiliary variables and interactions would be used in the imputation model. We have now specified a list of 9 candidate auxiliary variables and decided not to include interactions. We also provide more specificity regarding the number of datasets to be imputed (minimum 20) and the principles guiding decisions about the imputation process.

B2: Revised Analysis Plan

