primary analytic model covariates (child gender, child age at randomization, baseline BMI, treatment group) as well as auxiliary variables. Candidate auxiliary variables include child race / ethnicity, primary parent education, highest parental education, household income, family connector, parent BMI and 12m, 24m and 36m BMI. Some of the candidate auxiliary variables may be culled in consideration of factors such as the ratio of complete cases to estimated parameters and the degree of correlation with the outcome (Hardt et al., 2012). All analytic model covariates will have been documented prior to randomization with no missing values. Candidate auxiliary variables, excepting post-baseline BMI values and family connector, will have been measured at baseline with minimal missing values. The imputation model parameters may need to be calibrated in a manner that departs from the aforementioned expectations (i.e., number of imputations, number of iterations between datasets, number and coding of auxiliary variables). Model calibration will be informed by extant literature and guided by sensitivity analyses to arrive at a stable imputation model. The significance of the combined treatment parameter will not be a consideration in guiding imputation model decisions.

NET-Works: Linking families, communities and primary care to prevent obesity in preschool-age children

[name] ^{a,*}, [name] ^{b,1}, [name] ^{b,1}, [name] ^{a,2}, [name] ^{c,3}, [name] ^{a,2}, [name] ^{b,1}, [name] ^{a,b,1,2}

^a HealthPartners Institute for Education and Research, [name], USA

^b Division of Epidemiology and Community Health, School of Public Health, University of Minnesota, [name], USA

^c Department of Family Medicine and Community Health, University of Minnesota, [name], USA

CrossMark

ARTICLE INFO

Article history:

Received 11 June 2013

Received in revised form 24 September 2013

Accepted 26 September 2013

Available online 9 October 2013

Keywords:

Obesity prevention

Parent

Family

Community

Dietary intake

Physical activity

ABSTRACT

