2.3. Eligibility criteria and exclusions

Eligibility criteria are assessed on a telephone screening call and confirmed in person at the first data collection home visit. A child and his or her parent or primary caregiver are eligible for the study if: 1) the child is between ages of two and four years of age; 2) the child has no medical problems that would preclude study participation as determined by the primary care physician; 3) does not use any medications that would affect the child's growth; 4) the child's BMI is greater than or equal to the 50th percentile according to CDC age and sex reference standards with no upper limit [27]; 5) the family's income is below \$65,000 per year; 6) the child's parent agrees to participate in the study and does not plan to move out of the state in the next three years; 7) the parent or primary caregiver is willing and able to complete the evaluation measures and participate in intervention activities if assigned to the active intervention group; and 8) the parent or primary caregiver speaks either English or Spanish.

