Reach. The proportion of intended recipients who actually participate in an intervention; the extent to which the intervention is reaching the target population; could include, but not limited to, attendance, participation, and engagement by group (e.g. race, gender, SES, intervention group).

Intervention component	Construct(s)	Data collection method	Completed by	Timing of data collection
Well-child visit	Attendance, participation, and engagement by clinic, race, ethnicity	Similar to above measures, but examined by groups noted in previous column		
Home visits and check-in calls	Attendance, participation, and engagement by race, ethnicity	Similar to above measures, but examined by groups noted in previous column		
Parent class sessions and community events	Attendance, participation, and engagement by location, race, ethnicity	Similar to above measures, but examined by groups noted in previous column		

These analyses will be conducted using multiply imputed datasets. A fully conditional specification approach will be used for the imputation process, and will include in the imputation model all variables included in the primary analytic (scientific) model as well as interactions among them to improve the precision of the imputations. All covariates in the primary

analysis will have been measured at baseline prior to randomization and are therefore available for observed and unobserved BMI values. The random effects estimated in the primary analytic model will also be estimated in the imputation model [50]. The mechanisms that are likely to produce missing observations in the analytic dataset should result in

missing observations that are missing at random (MAR; e.g., early dropouts, busy schedule) or possibly missing not at random (MNAR; e.g., sporadic missing). The primary analytic models will be estimated from imputed datasets that assume all missing observations to be MAR. Sensitivity analyses will assess the severity of non-random missingness that would be necessary to reconsider the conclusions drawn from the primary analysis.

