Strengths of the NET-Works trial include the focus on preschool-age children at risk for obesity and their parents, a comprehensive evaluation protocol, the 3 year length of follow-up, and the multi-component, integrated intervention. The evaluation protocol includes measures of dietary intake, physical activity, the household food environment, the neighborhood environment, general and domain-specific parenting strategies, as well as measures of child cognitive development and novel measures of stress (i.e., hair cortisol). The comprehensive evaluation protocol will allow the impact

of the intervention to be evaluated on a wide range of outcomes, in addition to the primary focus on child BMI. Additionally, key moderators and mediators of the intervention will be explored. The NET-Works study includes detailed process evaluation measures developed in collaboration with the other COPTR sites. The process evaluation data will allow for examination of intervention fidelity, dose, and reach and the relationship between specific intervention components and study outcomes. The integration of the intervention components into existing and trusted settings where parents and children already spend time may increase the likelihood that if successful, the NET-Works intervention can be sustained and adopted widely within existing community parenting education and home visiting programs that include a national reach.

References

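### Imputing follow-up BMI without a treatment-by-baseline-BMI term leaves the intention-to-treat estimate open to a modest bias if both effect and dropout vary with baseline BMI; closing the gap is cheap

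*Protocol*

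**What the plan says.** The revised plan (A2, multiple imputation specifications) records the decision: "We have now specified a list of 9 candidate auxiliary variables and decided not to include interactions". It gives no reason.

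B2, 2.4.3 builds the imputation model from the "primary analytic model covariates (child gender, child age at randomization, baseline BMI, treatment group) as well as auxiliary variables". The nine candidates are race/ethnicity, two parental education variables, household income and "family connector, parent BMI and 12m, 24m and 36m BMI". The clause that allows later recalibration covers "i.e., number of imputations, number of iterations between datasets, number and coding of auxiliary variables"; interactions are not on that list. The primary model in B2, 2.4.1 likewise has one treatment coefficient and one baseline-BMI slope, and is to use all randomized participants.

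The design paper (2.10.1) had included model variables "as well as interactions among them to improve the precision of the imputations", and A2 acknowledges this: "We indicated previously that variables from the analytic model as well as auxiliary variables and interactions would be used in the imputation model". That text is superseded, and the change is not itself a fault. The same section of the paper says that the primary analysis assumes data missing at random.

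Two other places bear on the point. Children are eligible with BMI "greater than or equal to the 50th percentile according to CDC age and sex reference standards with no upper limit" (design paper, 2.3), and the Discussion says that "key moderators and mediators of the intervention will be explored".

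**The concern.** With main effects only, each missing BMI is imputed as if the intervention shifted every child by the same amount and BMI tracked identically in the two arms. With complete data from a randomized trial, an analysis model without an interaction still estimates the average effect over all randomized children, even when the effect varies between them. Imputation without the interaction loses that property: the shift it imputes is the one fitted to children who stayed. If those who leave differ in baseline BMI, and the effect depends on baseline BMI, the combined estimate leans toward the stayers' effect.

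Dropout that depends only on baseline BMI is missing at random, so the plan's own assumption does not exclude this. Matching the imputation model to the analysis model does not prevent it, and neither do more imputations or iterations. Family connector as an auxiliary allows different intercepts within the intervention arm, not different baseline-BMI slopes. At stake is the accuracy of the primary intention-to-treat estimate and, where the bias runs toward zero, some power.

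**Working it through.** **1. Scale, from the plan's own figures.** Inputs from the design paper, 2.10.2: 250 per arm, 15.6 dyads per cohort, ICC .02, cohort and child autocorrelations .30 and .40, 80% follow-up. Power of 80% is assumed, because the text does not state it.

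- Design effect = 1 + 14.6 × .02 = 1.292.
- r = (15.6 × .02 / 1.292) × .30 + (.98 / 1.292) × .40 = .376.
- Effective n, intervention = 250 / 1.292 / (1 - .376²) × .80 ≈ 180. Usual care = 250 / (1 - .40²) × .80 ≈ 238.
- SE of d = √(1/180 + 1/238) ≈ .0987.
- Detectable d = (2.241 + .842) × .0987 = .304 at alpha .025 (stated .305), and (1.960 + .842) × .0987 = .277 at alpha .05 (stated .277).

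The figures reproduce, so .099 SD is a fair yardstick. It reflects the parenting-class clustering of the design paper, not the family-connector clustering now planned.

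**2. Approximate bias.** Let γ be the change in effect per SD of baseline BMI, β the log-odds of dropout per SD (equal in both arms) and p the proportion missing. Children who stay have mean baseline BMI shifted by about -βp SD, so imputation without the interaction misses the average effect by about -γβp. It is zero if γ or β is zero, and changes sign if one of them does.

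**3. Simulation.** 1.5 million children per scenario; right-skewed baseline BMI; average effect -.30 SD; baseline-to-follow-up correlation .5; 20% missing, depending on baseline BMI only; 12-month BMI seen in none or half of the dropouts. The values of γ and the odds ratios are assumptions; the documents give none. A positive bias is toward zero.

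| γ | Odds ratio | -γ × ln(OR) × .20 | Bias, no interaction | Bias, with treatment × baseline BMI |
|---|---|---|---|---|
| -.1 | 1.5 | .008 | .008 | -.002 to .000 |
| -.1 | 2.0 | .014 | .013 to .015 | .000 |
| -.2 | 1.5 | .016 | .016 to .018 | .000 to .002 |
| -.2 | 2.0 | .028 | .027 to .030 | .000 to .001 |
| -.3 | 1.5 | .024 | .021 to .027 | -.001 to .000 |
| -.3 | 2.0 | .042 | .039 to .044 | -.001 |

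Against the yardstick this is .008/.0987 ≈ 0.1 to .044/.0987 ≈ 0.45 SE, or 3 to 15% of d = .30. A separate simulation with dropout log-odds slopes of .4 to .7 gave about .005 to .04 SD.

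**4. Variations.**

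- With γ = -.2 and odds ratio 1.5, the bias is about .012 at 15% missing and .017 to .023 at 25%.
- If dropout depends on baseline BMI in the intervention arm only, the bias is .003 to .026. If it runs in opposite directions by arm, the bias is at most .012.
- With 12-month BMI in 50 to 80% of dropouts and a 12-to-24-month correlation of .7 to .9 (assumed), γ = -.2 gives .005 to .017 instead of .018 (log-odds slope .5), and .008 to .023 instead of .030 (slope .8).
- A complete-case analysis with the primary model has nearly the same bias, so in this situation the imputation adds almost no protection.

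**5. Trial-sized check.** With 250 per arm, γ = -.20, slope .8 and 25% nominal missing: full data -.296, no-interaction imputation -.258, by-arm imputation -.297; SE .0923 against .0947 by arm. With 12-month BMI available for half of the dropouts, slope .5 and 20% missing: -.295, -.278 and -.295; SE .0872 against .0873.

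**6. Power.** At d = .30, alpha .025 and SE .0987, power at one time point is about 79%. A bias toward zero of .008 lowers it to about 76%, and .044 to about 64%.

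**The case against.** The best defence is that matching the imputation model to a prespecified additive analysis model is conventional, and that the bias needs two conditions the documents do not show. An entry range with no upper BMI limit shows neither effect modification nor BMI-related dropout. The bias is a fraction of a standard error; the top of the range needs a -.3 SD slope together with an odds ratio of 2, and follow-up BMI among the auxiliaries reduces it. If the intervention has no effect at any baseline BMI there is no bias, so false positives under that null are not inflated. All of this stands. It makes the point an improvement rather than the correction of a mistake.

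A reader might infer that moderator effects will be shrunk toward zero. In the simulations a treatment-by-baseline-BMI coefficient estimated from the no-interaction imputations came out at 63 to 75% of its true value (80 to 83% when dropout was unrelated to baseline BMI). But B2, 2.4.3 specifies imputation for the primary analysis, and nothing says that moderator analyses will use these datasets. The moderators and mediators listed in the design paper, 2.8.3, do not include baseline BMI. The shrinkage follows only if such an analysis is run on these imputations.

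One practical objection also stands. Every control family is its own family-connector group of one (B2, 2.4.1), so family connector cannot be an auxiliary in a control-only imputation model. Splitting by arm also roughly halves the cases per model, and 2.4.3 itself names the ratio of complete cases to parameters as a concern.

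**Conclusion.** The point holds as a conditional weakness. The plan imputes with one baseline-BMI slope for both arms. If the intervention effect and dropout both vary with baseline BMI, the primary estimate is biased under the plan's own missing-at-random assumption, by about .005 to .04 SD (up to roughly 0.4 SE) under the assumed values above. The direction is toward zero if the benefit and dropout both rise with baseline BMI, and it reverses if one of those relations reverses.

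The documents do not support saying that the primary result will be biased, that false positives are at risk, or that the move away from the design paper's interactions is an error. The case for changing the plan is that the protection costs almost nothing and, according to the Introduction, masking was still in place when the plan was written.

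**What to change.** In B2, 2.4.3, keep a single imputation model and add a sentence such as: the imputation model for each follow-up BMI will include treatment-by-baseline-BMI and treatment-by-earlier-follow-up-BMI terms, which will not be removed during calibration. The A2 statement on interactions would change to match.

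The alternative is to run the fully conditional specification separately by arm, with family connector used only in the intervention-arm model, and then combine the arms for the primary models. With 265 intervention families and 75 to 85% follow-up, about 199 to 225 would be observed in that arm (265 × .75 and 265 × .85). With the planned 250 controls, about 188 to 213 would be.

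The cost is one sentence and a small code change before unmasking. In simulation the standard error rose by about 0.5% with the added treatment-by-baseline-BMI term, about 1% with by-arm imputation and six extra covariates, and at most 3% in the smaller simulations. Those runs did not carry the full auxiliary list or the clustering, so the cost should be confirmed on the simulated rehearsal data that the investigators already hold. There are also fewer cases per imputation parameter, especially by arm; the single-model version is preferable if that ratio is tight.

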2.1. Study Design

The study is an individually randomized group trial. Families will be randomized equally to the NET-Works intervention or a control group. The NET-Works intervention duration is thirty-six months. Outcome measures will be assessed at baseline and at 12, 24 and 36 months post-randomization.

2.2. Primary Research Question and Hypothesis

Specific Aim 1

To evaluate the effects of a three-year multi-setting parent-targeted randomized controlled intervention on the primary outcome, child BMI, compared to a standard primary care-only intervention among low income ethnic minority two to four year old children who are at or above the 50th percentile of BMI for age and gender.

Hypothesis 1: Children in the multi-setting parent-targeted intervention will have a lower BMI at 24 and 36 months, compared with children in the standard primary care only control group.

2.4. Primary Analysis

2.4.1. Statistical model and approach

The primary analysis will test whether NET-Works participants have lower BMI at 24 and 36 months relative to comparison participants. We will use data from all randomized participants (intent to treat approach) to estimate two mixed models in which 24 or 36 month BMI values are predicted from randomized treatment group with age group at baseline, sex and BMI at baseline as covariates, and a random intercept for family connector (u_{0j}):

$$\text{BMI}_{ij} = \gamma_{00} + \gamma_{01}\text{NET-Works}_j + \gamma_{20}\text{3yo}_i + \gamma_{30}\text{4yo}_i + \gamma_{40}\text{female}_i + \gamma_{50}\text{BMI baseline}_i + [u_{0j} + e_{ij}].$$

We will conclude that NET-Works was efficacious if the γ_{01} parameter in both mixed models is statistically significant and negative, meaning that BMI is significantly lower among NET-Works children than comparison children.

[figure not shown]
A source of dependence lies in the family connector (FC) assignment. Seven family connectors delivered the home visit component of NET-Works to intervention families. To the extent FC assignments were intended to be culture-specific, and FCs may vary slightly in their manner of delivering intervention content to the families with whom they work, dependence may be introduced through common FC assignment. As such, it will be important to account for dependence in BMI introduced through FC assignment.

Each of the families will be assigned to a FC group based on the primary FC with whom they worked. Treatment group families that did not participate in the home visit intervention component, and all control group families, will be assigned to their own n=1 FC group following the method of Esserman et al. (2012).

2.4.3. Missing data including level of attrition, loss to follow-up, and missing data treatment

The primary analysis will be conducted using multiply imputed data. We plan to use fully conditional specification to impute sporadically missing followed by 12, 24 and 36 month monotonically missing BMI values. We anticipate imputing a minimum of 20 datasets based on the observed missingness to date in post-baseline BMI values but may upwardly adjust this number to ensure adequate power (Graham et al., 2007). The imputation model will include the

primary analytic model covariates (child gender, child age at randomization, baseline BMI, treatment group) as well as auxiliary variables. Candidate auxiliary variables include child race / ethnicity, primary parent education, highest parental education, household income, family connector, parent BMI and 12m, 24m and 36m BMI. Some of the candidate auxiliary variables may be culled in consideration of factors such as the ratio of complete cases to estimated parameters and the degree of correlation with the outcome (Hardt et al., 2012). All analytic model covariates will have been documented prior to randomization with no missing values. Candidate auxiliary variables, excepting post-baseline BMI values and family connector, will have been measured at baseline with minimal missing values. The imputation model parameters may need to be calibrated in a manner that departs from the aforementioned expectations (i.e., number of imputations, number of iterations between datasets, number and coding of auxiliary variables). Model calibration will be informed by extant literature and guided by sensitivity analyses to arrive at a stable imputation model. The significance of the combined treatment parameter will not be a consideration in guiding imputation model decisions.

NET-Works: Linking families, communities and primary care to prevent obesity in preschool-age children

[name] ^{a,*}, [name] ^{b,1}, [name] ^{b,1}, [name] ^{a,2}, [name] ^{c,3}, [name] ^{a,2}, [name] ^{b,1}, [name] ^{a,b,1,2}

^a HealthPartners Institute for Education and Research, [name], USA

^b Division of Epidemiology and Community Health, School of Public Health, University of Minnesota, [name], USA

^c Department of Family Medicine and Community Health, University of Minnesota, [name], USA

CrossMark

ARTICLE INFO

Article history:

Received 11 June 2013

Received in revised form 24 September 2013

Accepted 26 September 2013

Available online 9 October 2013

Keywords:

Obesity prevention

Parent

Family

Community

Dietary intake

Physical activity

ABSTRACT

Obesity prevention in children offers a unique window of opportunity to establish healthful eating and physical activity behaviors to maintain a healthful body weight and avoid the adverse proximal and distal long-term health consequences of obesity. Given that obesity is the result of a complex interaction between biological, behavioral, family-based, and community environmental factors, intervention at multiple levels and across multiple settings is critical for both short- and long-term effectiveness. The Minnesota NET-Works (Now Everybody Together for Amazing and Healthful Kids) study is one of four obesity prevention and/or treatment trials that are part of the Childhood Obesity Prevention and Treatment (COPTR) Consortium. The goal of the NET-Works study is to evaluate an intervention that integrates home, community, primary care and neighborhood strategies to promote healthful eating, activity patterns, and body weight among low income, racially/ethnically diverse preschool-age children. Critical to the success of this intervention is the creation of linkages among the settings to support parents in making home environment and parenting behavior changes to foster healthful child growth. Five hundred racially/ethnically diverse, two-four year old children and their parent or primary caregiver will be randomized to the multi-component intervention or to a usual care comparison group for a three-year period. This paper describes the study design, measurement and intervention protocols, and statistical analysis plan for the NET-Works trial.

© 2013 Elsevier Inc. All rights reserved.

1. Introduction

Nearly one-third of preschool-age children are overweight or obese [1]. Racial/ethnic minority and lower socioeconomic

status children are at even greater risk for obesity [2]. The preschool years provide a unique window of opportunity to establish healthful eating and physical activity behaviors [3]. Given the complex etiology of childhood obesity, multi-level, multi-setting interventions are critical for effectiveness [4]. Interventions that directly engage parents and impact the home environment are needed given that the largest obesity prevention interventions have been school-based with limited parental involvement [5–9]. One strategy to more effectively engage parents in obesity prevention efforts is to consider the types of organizations and community-based programmatic initiatives utilized and valued by parents. Integrating strategies that promote healthy eating and activity patterns into settings where parents already spend their time could lead to the development of interventions with high potential for

^{*} ClinicalTrials.gov Identifier: NCT01606891.

^{1,2} This study is supported by a grant from the Eunice Kennedy Shriver National Institute of Child Health and Human Development (U01HD068990).

* Corresponding author at: HealthPartners Institute for Education and Research, [name], USA. [contact].

E-mail address: [contact] ([name]).

¹ [contact].

² [contact].

³ [contact].

dissemination and sustainability. Three examples include public health nurse home-visiting, community-based parenting classes, and pediatric primary care.

Public health nurse home-visiting programs provide health and psychosocial-related services to at-risk pregnant women and young mothers [10–15]. National early childhood parent education programs also offer home-visiting models [16,17]. Recently, the nurse home-visiting model was evaluated for obesity prevention in infants in a randomized controlled trial [18,19]. The Parents As Teachers Program also evaluated a parent-targeted home-based intervention to increase child fruit and vegetable intake [20]. Results suggest home-visiting holds promise for obesity prevention.

Community parenting classes are also widely available and appeal to parents of preschool-age children from diverse backgrounds. Parenting classes promote child school readiness through building parenting skills and social support networks. Healthful food choices, active play, and screen time topics align well with parenting class curriculum and could be readily incorporated into existing parent-focused community-based programs.

Primary care is a third important setting through which parents of preschool-aged children may be reached [21]. Primary care providers are influential sources of health information who can help parents promote and reinforce child behaviors related to healthful eating, activity patterns, and body weight. The primary care setting represents a unique intervention opportunity for direct, parent-focused child obesity prevention [21].

In addition to these well-established systems, the neighborhood environment provides resources that can enhance or detract from parent efforts to support optimal child growth [22–26]. Without access to these resources, parents face significant barriers to adopting eating and activity-related behavioral intervention messages. Thus, obesity prevention interventions need to identify and connect parents to existing neighborhood resources.

The goal of the Minnesota NET-Works (Now Everybody Together for Amazing and Healthful Kids) study is to integrate home, community, primary care and neighborhood intervention strategies to prevent obesity among ethnically diverse preschool-age children. The NET-Works trial is one of two unique prevention trials that are part of the Childhood Obesity Prevention and Treatment Research (COPTR) consortium, a National Heart, Lung, and Blood Institute (NHLBI)- and National Institute of Child Health and Human Development (NICHD)-sponsored collaborative effort to develop and test novel approaches to prevent or treat childhood obesity. Each field center is testing distinct interventions with unique populations and eligibility criteria, but share a core set of common measures and protocols. This paper describes the NET-Works trial study design, measurement and intervention protocols, and statistical analysis plan.

2. Materials and methods

